5.3. Inclusion and Exclusion Criteria for PegIFN

Participants who permanently discontinue GSK3228836 due to a liver stopping event (Section 7.1.1) are not eligible for treatment with PegIFN.

Participants who had GSK3228836 dosing held or whose dose was reduced due to Protocol defined liver monitoring criteria (Section 7.1.1) are eligible for PegIFN treatment only if:

- a. ALT is $<5 \times \text{ULN}$ and bilirubin/INR are \leq baseline or ULN (whichever is higher) at PegIFN eligibility assessment
AND
- b. Additional lab assessments performed do not suggest drug-induced liver injury (DILI) or other condition contraindicated for treatment in the PegIFN label.

For participants who do not meet both of these criteria, eligibility for PegIFN should be determined by the investigator based upon a risk/benefit assessment and the following PegIFN eligibility criteria (Table 8).

Note: If local prescribing PegIFN guidelines are more stringent than the criteria below, follow the most stringent criteria.

- ALT $<5 \times \text{ULN}$
- Platelets $>90 \times 10^9/\text{L}$
- Absolute Neutrophil Count (ANC) $>1.5 \times 10^9/\text{L}$
- Haemoglobin $\geq 10 \text{ g/dL}$

In addition:

- TSH + T4 should be confirmed to be normal and/or adequately controlled
- The absence of severe psychiatric condition
- An ophthalmologic examination should have been conducted at screening (or results from a prior ophthalmological examination within 3 months of screening should have been available).

Table 8 Eligibility Criteria to start PegIFN

Baseline Laboratory Assessment	Inclusion Criteria
i) Platelets	$>90 \times 10^9 \text{ cells/L}$
ii) ANC	$>1.5 \times 10^9 \text{ cells/L}$
iii) Haemoglobin	$>10 \text{ g/dL}$
iv) ALT	$<5 \times \text{ULN}$
v) TSH/T4	Within normal range or adequately controlled
vi) Neuropsychiatric Assessment	No severe psychiatric condition
vii) Ocular Exam	No condition contraindicated for PegIFN, however periodic examinations maybe required based upon screening assessment (refer to Section 8.2.2)

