PAXGene RNA for expression analysis in whole blood	X						X							X
OPTIONAL: Genetics	X													

Day	1	4	8	11	15	22	29	36	43	50	57	64	71	78
Week	1	1	2	2	3	4	5	6	7	8	9	10	11	12
Window (days)	±1 day				±2	±3 days								
Archived Samples [serum; plasma]	X				X		X		X		X		X	

1. A WOCBP must have both a confirmed menstrual period prior to the first dose of study intervention AND a negative highly sensitive pregnancy test [urine or serum] within 24 hours before the first dose of study treatment (locally performed)
2. Only for selected sites able to transport to the analysis lab as specified in the SRM
3. ECG to be conducted at any point from Week 11 and prior to initiation of PegIFN

Table 4 PegIFN Treatment Period

Participants will be assessed using Column 1 below to determine eligibility to begin treatment with PegIFN and moved to the “Yes” column based on the eligibility criteria outlined in Section 5.3. If a participant is determined to be **eligible** for PegIFN dosing, they will begin PegIFN Dosing on Week 1. If a participant is determined to be **ineligible** for PegIFN, see Table 5.

PegIFN Dosing Week	1 ^a	2	3	4	5	6	7	8	9	10	11	12	13	14	15	16	17	18	19	20	21	22	23	24	
Window	±3 days																								
Confirmed Eligibility for Peg-IFN	Confirm PegIFN Eligibility ¹	Yes ²																							
Clinic visit ³	X		X	X	X		X		X		X		X		X		X		X		X		X		X
Peg-IFN dosing		X	X	X	X	X ³	X	X ³	X	X ³	X	X ³	X ³	X	X ³	X ³	X	X ³	X ³	X ³	X	X ³	X ³	X ³	X
Safety Assessments																									
AE/SAE review	X		X	X	X	X	X	X	X	X	X	X	X	X	X	X	X	X	X	X	X	X	X	X	X
Concomitant medication review	X		X	X	X	X	X	X	X	X	X	X	X	X	X	X	X	X	X	X	X	X	X	X	X
Symptoms directed exam	X				X				X				X			X				X					
Vital signs	X		X	X	X		X		X		X		X		X		X		X		X		X		X
Injection site reactions		X	X	X	X		X		X		X		X		X		X		X		X		X		X
Neuropsychiatric assessment (C-SSRS and BDI-II)	X		X	X	X		X		X		X		X		X		X		X		X		X		X
Laboratory Assessments																									
Pregnancy test (WOCBP)		X			X				X		X			X			X				X				X
Haematology [includes platelet and WBC with differential] ⁴		X	X	X	X		X		X		X		X		X		X		X		X		X		X
TSH, T4						X							X												X
PT, INR, aPTT		X			X								X			X					X				X
Chemistry		X	X	X	X		X		X		X		X		X		X		X		X		X		X
Urinalysis		X	X		X				X				X			X				X				X	
Urine ACR		X	X		X				X				X			X				X				X	
HBsAg and HBV DNA		X	X	X	X		X		X		X		X		X		X		X		X		X		X
Anti-HBsAg and anti-HBeAg		X			X				X				X			X				X				X	

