5.1. Inclusion Criteria

AGE
1. At least 18 to 75 years of age at the time of signing the informed consent [if country/site age requirements for consent differ, the more stringent (e.g., higher age) restriction will be required for that country/site].
TYPE OF PARTICIPANT AND DISEASE CHARACTERISTICS
2. Participants who are eligible to be treated with PegIFN (Table 8)
3. Documented chronic HBV infection ≥ 6 months prior to screening AND currently receiving stable NA therapy except telbivudine, defined as no changes to their NA regimen from at least 6 months prior to screening and with no planned changes to the stable regimen over the duration of the study
4. Plasma or serum HBsAg concentration > 100 IU/mL
5. Plasma or serum HBV DNA < 90 IU/mL
6. Alanine Transaminase (ALT) ≤ 2 X ULN

SEX
7. Male and/or Female 
 a. A male participant is eligible to participate if they agree to the following during the intervention period and for at least 90 days after the last dose of study treatment 
 i. Refrain from donating sperm ii. AND be abstinent from heterosexual intercourse as their preferred and usual lifestyle (abstinent on a long term and persistent basis) and agree to remain abstinent OR Must agree to use contraception/barrier as detailed below 
 1. Agree to use a male condom [and should also be advised of the benefit for a female partner to use a highly effective method of contraception as a condom may break or leak] when having sexual intercourse with a woman of childbearing potential who is not currently pregnant b. A female participant is eligible to participate:

- i. If she is not pregnant or breastfeeding
 - ii. AND at least one of the following conditions applies:
 1. Is not a woman of childbearing potential (WOCBP) as defined in Section 10.4 Contraception and Barrier Guidance
 2. Is a WOCBP and using a contraceptive method that is highly effective (with a failure rate of <1% per year), preferably with low user dependency during the intervention period and for at least 90 days after the last dose of study treatment
- A WOCBP must have a negative highly sensitive pregnancy test (urine or serum as required by local regulations) within 24 hours before the first dose of study intervention, see Section 10.2.

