ALT \geq 12 x ULN and Bilirubin \leq 1.5 x ULN and INR \leq 1.5 (if available)	Hold dose Monitor twice weekly Additional lab assessments if not already done Take off hold: GSK3228836 150 mg SC weekly when ALT < 10 x ULN; increasing dose to 300 mg (if applicable) should be agreed with Medical Monitor	Permanently discontinue IMP if any of the following apply: 
 • ALT \geq 10 x ULN > 4 weeks • ALT \geq 12 x ULN recurs after IMP taken off hold
ALT \geq 3 x ULN and 1.5 x ULN < bilirubin \leq 2 x ULN (>35% direct) and INR \leq 1.5 (if available)	Hold dose Monitor twice weekly Additional lab assessments if not already done Take off hold: GSK3228836 150 mg SC weekly when bilirubin returns to < 1.5 x ULN; increasing dose to 300 mg (if applicable) should be agreed with Medical Monitor	Permanently discontinue IMP if the following recurs after IMP taken off hold: 1.5 x ULN < bilirubin \leq 2 x ULN (>35% direct) And INR \leq 1.5 (if available)
ALT \geq 3 x ULN and any of the following apply: 
 • bilirubin > 2 x ULN (>35% direct) • associated with the appearance or worsening of hepatitis symptoms • INR > 1.5 (if available) 		Permanently discontinue IMP Monitor twice weekly until stable ALT Additional lab assessments if not already done

ALT = alanine aminotransferase; IMP = investigational medicinal product; ULN = upper limit of normal

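### Protocol 5.3 makes PegIFN after a liver-related GSK3228836 hold conditional on bilirubin, INR and DILI checks, then gives those who fail them a route without these checks

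*Protocol*

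**What the plan says.** Protocol 5.3 sets out three steps.

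1. A permanent liver stop bars PegIFN: "Participants who permanently discontinue GSK3228836 due to a liver stopping event (Section 7.1.1) are not eligible for treatment with PegIFN".
2. Participants whose GSK3228836 was held or reduced under the liver monitoring criteria "are eligible for PegIFN treatment only if" two conditions both hold. Condition (a) is ALT below 5 x ULN, with bilirubin and INR no higher than the larger of baseline and ULN. Condition (b) is that additional laboratory work does not suggest DILI or another contraindication in the PegIFN label.
3. The next sentence begins "For participants who do not meet both of these criteria, eligibility for PegIFN should be determined by the investigator". It bases that decision on a risk/benefit assessment and Table 8.

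Table 8 and the bullets before it cover platelets, neutrophils, haemoglobin, ALT, thyroid function, psychiatric state and the eye examination.

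Table 8 is not written only for people with liver events. Inclusion criterion 2 in Protocol 5.1 applies it at entry, and the introduction to Table 4 in Protocol 1.3 moves every participant to dosing "based on the eligibility criteria outlined in Section 5.3".

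In Table 9 (Protocol 7.1.1) a bilirubin hold is released to "GSK3228836 150 mg SC weekly when bilirubin returns to < 1.5 x ULN".

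**The concern.** An only-if rule states what is necessary. A route for those who fail it cancels the rule. The route offered here also drops the items that make (a) and (b) liver-specific.

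Two sites that both follow the text could decide differently on starting PegIFN in the same kind of participant: one with a recent liver-related hold whose bilirubin or INR is still raised, or whose tests suggest DILI. The amendment summary says this text was added to clarify eligibility after liver hold or stopping criteria, at the FDA's request. As it stands, it does not give sites one answer.

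**Working it through.** The plan gives no figure to reproduce. The check sets the two rules side by side and then works out who falls between them.

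**Step 1. Compare the criteria (Protocol 5.3).**

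| Item | Conditions (a) and (b) | Table 8 and bullets |
|---|---|---|
| ALT | < 5 x ULN | < 5 x ULN |
| Bilirubin | <= max(baseline, ULN) | none |
| INR | <= max(baseline, ULN) | none |
| DILI | must not be suggested | none |
| Label contraindication | must not be suggested | eye examination row only |

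Only the ALT limit carries over in full.

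**Step 2. Test one illustrative participant.** The dose is on hold under the bilirubin row of Table 9 when planned dosing ends. ALT is 4 x ULN and bilirubin 1.8 x ULN (more than 35% direct). INR is normal, baseline bilirubin is at or below ULN, and every Table 8 item is met.

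- Only-if rule: 1.8 > 1.0, so (a) fails and the participant is not eligible.
- Next sentence: ALT 4 < 5 and all Table 8 rows pass, so the investigator may judge the participant eligible.

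**Step 3. Find the bilirubin range in which the two rules differ.** Let M = max(baseline, ULN). Table 8 sets no upper limit, so the rules differ for any bilirubin above M that has not led to a permanent stop.

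- *Lifted bilirubin hold.* Entry is at ALT >= 3 x ULN with bilirubin above 1.5 and up to 2 x ULN (more than 35% direct). Release is below 1.5 x ULN. If bilirubin then stays below the release level, the gap runs from M to 1.5 x ULN. With baseline at or below ULN this is > 1.0 to < 1.5 x ULN. With baseline at 1.25 x ULN (the highest screening value in exclusion criterion 21g that needs no Medical Monitor discussion) it is > 1.25 to < 1.5 x ULN.
- *ALT hold.* The row for ALT >= 12 x ULN allows bilirubin up to 1.5 x ULN, so the same participant can be above M once ALT has fallen below 5 x ULN.
- *Hold still open when planned dosing ends.* Bilirubin can be up to 2 x ULN. It can be higher if ALT is below 3 x ULN or the direct fraction is 35% or less, because the permanent-stop row for bilirubin needs ALT >= 3 x ULN, bilirubin > 2 x ULN and more than 35% direct together.
- *INR.* The hold rows allow INR up to 1.5, while (a) requires INR at or below max(baseline, ULN). The documents give no ULN for INR, so this gap cannot be put in numbers.

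**Step 4. Cost in doses of holding to the strict rule (Protocol 1.3, Table 6).** Doses lost = 24 minus doses remaining.

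| Eligible at Week | Doses remaining | Doses lost | Share of 24 |
|---|---|---|---|
| 2 | 23 | 1 | 4.2% |
| 3 | 22 | 2 | 8.3% |
| 4 | 21 | 3 | 12.5% |
| 6 | 19 | 5 | 20.8% |
| 8 | 17 | 7 | 29.2% |
| 10 | 15 | 9 | 37.5% |
| 13 | 12 | 12 | 50.0% |

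A participant who still fails at Eligibility Week 13 receives no PegIFN (Protocol 4.1), so 24 of 24 doses are lost.

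**The case against.** **The sentence can be read without contradiction.** The two criteria it mentions could be the two liver situations above it (permanent stop; hold or reduction), so that Table 8 is introduced for everyone else. This is probably what was meant, given that Table 8 applies to all. But the nearest pair is (a) and (b), and the text ties Table 8 to those who fail that pair. On this reading too, the sentence has to be rewritten.

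**Other controls exist.** This stands in part.

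- Protocol 4.1 bases re-assessment on the label, and Table 4 (footnote 2) and Table 5 both point to 4.1. Stricter local prescribing rules also take precedence. Neither the label nor the local rules are among the documents, so they may impose a hepatic limit.
- Protocol 7.2.2 stops PegIFN at once for ALT rises that come with increased bilirubin or hepatic decompensation, but only after PegIFN has begun.
- Liver monitoring under 7.1.1 may end when values merely stabilise, and immediate safety concerns go to the sponsor (Protocol 8).

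None of these puts the bilirubin/INR limit of (a) back into the protocol text before the first PegIFN dose.

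**A reader might infer more than the documents support:**

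- That the sponsor deliberately waived liver safeguards. The permanent-stop bar and the ALT limit remain, and the likelier explanation is a misplaced reference.
- That participants were in fact started on PegIFN in this state. No counts are given.
- That the primary analysis is compromised. The main estimand handles PegIFN ineligibility by treatment policy.

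**Conclusion.** The contradiction is real as written. It concerns participants who had a liver-related hold or dose reduction without a permanent liver stop, who meet Table 8 and any stricter label or local rule, and who have bilirubin or INR above max(baseline, ULN) or tests suggesting DILI. The band of > 1.0 to < 1.5 x ULN describes lifted bilirubin holds with baseline at or below ULN. It is not the full range, because open holds can go beyond it. How many participants fall in this group cannot be derived from the documents.

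This is a narrow fault in a safety rule that should be corrected. It does not alter the definition of the main estimand, but it is not wholly without efficacy consequences: who starts PegIFN, and when, determines exposure and who enters the PegIFN-duration and at-least-12-dose supplementary estimands (SAP 4.2.4.2 and 4.2.4.3).

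The conclusion rests on the plain wording of 5.3 and on the absence of bilirubin, INR and DILI items from Table 8. It assumes nothing about the content of the label.

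**What to change.** Replace the sentence in Protocol 5.3 with:

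> Participants with a liver-related hold or dose reduction who do not meet both (a) and (b) are not eligible to start PegIFN at that assessment and are re-assessed per Table 5; isolated unconjugated bilirubin above baseline in known benign hyperbilirubinaemia (e.g. Gilbert syndrome) is to be discussed with the Medical Monitor. All participants must also meet every criterion in Table 8, and the investigator must judge the risk/benefit acceptable.

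The Medical Monitor clause follows existing practice in exclusion criterion 21g and the notes to Table 9. Without it, a participant with Gilbert syndrome held for ALT could be refused for a harmless fluctuation. The last sentence keeps Table 8's thresholds fixed and adds the investigator's judgement to them, so that judgement cannot replace them.

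The editorial cost is one replacement text, by amendment or clarification letter, using re-assessment visits that already exist. The clinical cost is the lost exposure in Step 4, which may slightly lower response. It also shifts participants between the duration groups: eligibility at Week 6 leaves 19 doses, short of the 20-week group. Eligibility at Week 13 leaves exactly 12, so one missed dose removes the participant from the at-least-12-dose analysis.

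Timing matters. The projection table in SAP 4.7 has 47 + 53 = 100 participants at off-treatment Week 24 by the January 2023 review. If PegIFN dosing is complete, document the intended rule and list any participant started under this sentence.

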5.4. Lifestyle Considerations

5.4.1. Alcohol and Tobacco

During each dosing session, participants will abstain from alcohol for 24 hours before the start of each scheduled clinic visit until after they leave the clinic.

Participants who use tobacco products will be instructed that use of nicotine-containing products (including nicotine patches and other delivery devices such as vaporisers) will not be permitted while they are in the clinical unit.

5.4.2. Activity

Participants will abstain from strenuous exercise for 48 hours before each blood collection for clinical laboratory tests. For the duration of the study, until final follow-up, participants are encouraged to refrain from changing their activity beyond that which they normally perform. Additionally, participants will abstain from taking creatine-containing exercise supplements for all parts of the study.

5.5. Screen Failures

Screen failures are defined as participants who consent to participate in the clinical study but are not subsequently randomised. A minimal set of screen failure information is required to ensure transparent reporting of screen failure participants to meet the Consolidated Standards of Reporting Trials publishing requirements and to respond to queries from regulatory authorities. Minimal information includes demography, screen failure details, eligibility criteria, any protocol deviations and any serious adverse events (SAEs).

Individuals who do not meet the criteria for participation in this study (screen failure) may not be rescreened unless discussed and agreed with the Medical Monitor. Individuals who fall out of the screening window, may be rescreened at the discretion of the investigator and site.

5.6. Criteria for Temporarily Delaying Administration of Study Intervention

See Section 7.1 for guidance on treatment hold and criteria for temporarily delaying GSK3228836 and/or PegIFN.

6. STUDY INTERVENTION(S) AND CONCOMITANT THERAPY

Study intervention is defined as any investigational intervention(s), marketed product(s), placebo, or medical device(s) intended to be administered to a study participant according to the study protocol.

6.1. Study Intervention(s) Administered**Study Treatment**

Study Treatment		
Product Name:	GSK3228836	PegIFN
Formulation Description:	Clear colourless to slightly yellow solution	Injection for subcutaneous use. The commercial product is used unmodified, except a label is applied to indicate clinical investigational use.
Dosage Form:	Solution for injection	Solution for injection
Unit Dose Strength(s)/Dosage Level(s):	150 mg/mL; 1.0 mL nominal volume per vial (minimal overfill per vial)	180 mcg/0.5 mL; pre-filled syringe
Route/Administration/Duration:	SC, multiple (once weekly up to 24 weeks, plus loading doses)	180 mcg/week, SC, up to 24 weeks
Dosing Instructions:	Administer two SC injections for 300 mg dose.	Administer SC injection; refer to label
Manufacturer/Source of Procurement:	GSK GlaxoSmithKline Manufacturing SpA, Parma (Italy)	F Hoffmann-La Roche AG, [name].
Method for Individualising Dosage	Dispensing into syringes	Pre-filled syringe that contains graduation marks corresponding to 180 micrograms (mcg), 135 mcg and 90 mcg

SC=subcutaneous;

GSK3228836 injection instructions

The site of GSK3228836 injection will be recorded for each participant and dose(s). Sites of GSK3228836 injection are listed in order of preference and are a guide for the clinical staff.

1. Abdominal quadrants
2. Thighs
3. Outer area of the upper arms
4. Buttocks

GSK3228836 injections should be rotated within each anatomical site or site(s) of injection should be changed administration-to-administration. Injection into areas with ongoing injection site reactions should be avoided.

PegIFN injection instructions

PegIFN is administered by subcutaneous injection in the abdomen or thigh. PegIFN should be inspected visually for particulate matter and discoloration before administration, and not used if particulate matter is visible or product is discoloured.

A participant may self-inject PegIFN only if the physician determines that it is appropriate, and the patient agrees to medical follow-up as necessary and has been trained in proper injection technique.

Discard the unused portion in excess of the labelled volume. Use only one vial or prefilled syringe or disposable auto-injector per dose.

6.2. Preparation/Handling/Storage/Accountability

The investigator or designee must confirm appropriate temperature conditions have been maintained during transit for all study intervention received and any discrepancies are reported and resolved before use of the study intervention.

Only participants enrolled in the study may receive study intervention and only authorised site staff may supply or administer study intervention. All study interventions must be stored in a secure, environmentally controlled, and monitored (manual or automated) area in accordance with the labelled storage conditions with access limited to the investigator and authorised site staff.

The investigator, institution, or the head of the medical institution (where applicable) is responsible for study intervention accountability, reconciliation, and record maintenance (i.e., receipt, reconciliation, and final disposition records).

Further guidance and information for the final disposition of unused study intervention are provided in the Study Reference Manual (SRM).

Under normal conditions of handling and administration, study intervention is not expected to pose significant safety risks to site staff. Take adequate precautions to avoid direct eye or skin contact and the generation of aerosols or mists. In the case of unintentional occupational exposure notify the monitor, Medical Monitor and/or GSK study contact.

A Material Safety Data Sheet (MSDS)/equivalent document describing occupational hazards and recommended handling precautions either will be provided to the investigator, where this is required by local laws, or is available upon request from GSK.

6.3. Measures to Minimise Bias: Randomisation and Blinding

All participants will be centrally randomised using an Interactive Voice/Web Response System (IVRS/IWRS). Before the study is initiated, the telephone number and call-in directions for the IVRS and/or the log in information and directions for the IWRS will be provided to each site.

Study intervention will be dispensed at the study visits summarised in the SoA. Returned study intervention should not be re-dispensed to the participants.

Participants will be randomised in a 1:1 ratio to receive study intervention. Investigators and the participants will be unblinded to study intervention throughout the course of the study. Allocation will be concealed by central blocking to protect against foreknowledge of allocation pre-randomisation.

GSK is unblinded however the risk of potential bias will be mitigated by the following steps:

- Dummy randomisation schedule will be used by Biostatistics during preparatory programming activities, although this will not completely mask treatment assignment due to the different visit/regimen schedules for each arm.
- Where feasible, limit the central teams exposure to virological biomarkers including HbsAg, HbsAb and HBV DNA.

- Details will be included in separate blinding plans.

Unblinded monitors and, in the event of a Quality Assurance audit, the auditor(s) will be allowed access to unblinded study intervention records at the site(s) to verify that randomisation/dispensing has been done accurately.

GSK's Clinical Safety Department staff may reveal the treatment allocation for any participant with an SAE. If the SAE requires that an expedited regulatory report be sent to one or more regulatory agencies, a copy of the report, identifying the participant's intervention assignment, may be sent to investigators in accordance with local regulations and/or GSK policy.

